## 4. DATA

## 4.1. Dataset Preparation

The analysis dataset for the final population PK analysis (see Section 5) will be based on source data from SDTM or Analysis Data Model (ADaM) domains. It will be assumed that comprehensive checks have been performed and that source file contents accurately reflect collected clinical study data. Physiologically relevant covariates will be included in the dataset, with particular reference to those identified as clinically relevant based on the latest version of the population PK model (see Section 1.1.3).

The datasets will be assembled as analysis-ready files (\*.csv) using Statistical Analysis System (SAS®, Version 9.4) or R (R Core Team (2018). R: A language and environment for statistical computing. R Foundation for Statistical Computing, Vienna, Austria, URL https://www.R-project.org/), according to appropriate data specifications. If datasets are modified over the course of the analysis, the file name of each version will be unique. This will allow for verification of the different datasets used in each population PK analysis file. For each unique participant, the dataset will include drug dosing history, concentrations with associated sampling times, demographic variables, relevant covariates and any other relevant information.

Quality control (QC) checks will be performed to ensure that all datasets are accurate and reflect the analysis population specified in this analysis plan. All QC processes will be conducted by an independent reviewer to confirm that there are no inconsistencies either in source databases or in scripts used to generate analysis-ready files.

## 4.2. Evaluable Participants

A participant will be included in the analysis if the following criteria are satisfied:

- The participant has at least one measurable observation (daprodustat concentration) with an associated sampling time.
- The participant has relevant dosing data prior to each measurable concentration.
- The participant is not associated with a protocol violation that could confound interpretation of the analysis.

## 4.3. Data Handling

Data records may be considered for exclusion based on the following reasons:

- The value is inconsistent with that for other individuals or with the chronological sequence of study procedures and cannot be resolved through a query resolution process.
- The value does not have adequate supporting information to allow for reasonable and unique assignment as a participant observation.
- The value is associated with documented errors in drug administration, specimen collection, sample handling, or bioanalytical procedures, and may reasonable be expected to produce spurious results.

Page 14 of 22

• The value has been carefully considered and identified as an outlier (see Section 4.3.5).

A listing of all missing and excluded data, together with a reason for their exclusion will be provided as an appendix to the population PK analysis report(s).

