## 9.2. Analysis Sets

For purposes of analysis, the following participant analyses sets are defined:

Participant	Definition/Criteria
Analyses Sets	
Screened	All participants who had a valid ICF and were screened for eligibility.
Enrolled	All participants who entered the study (who received study intervention or underwent a post screening study procedure).
	Note: screening failures (who never passed screening even if rescreened) and participants screened but never enrolled into the study (met eligibility but not needed) are excluded from the Enrolled analysis set as they did not enter the study.
Safety	All participants in the Enrolled analysis set who take at least 1 dose of study intervention (daprodustat).
	The Safety analysis set will be used for Main Study summaries including: study population, safety, efficacy (Hgb) and other health outcomes of interest.
Integrated PK	All participants in the Safety analysis set who participated in the Integrated PK Phase of the study and who had at least 1 nonmissing PK assessment (non-quantifiable values will be

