## 4.3.5. Handling of Outlier Data

Prior to population PK analysis, graphical inspection will be conducted of individual or pooled concentration-time profiles to identify outlier or anomalous data. Additionally, the PK data may be plotted relative to each analysis participant's actual dosing history to detect any anomalies. Following preliminary model runs, concentrations for which the absolute value of conditional weighted residuals (CWRES) are greater than 6 (|CWRES > 6|) will be flagged as questionable. These data may be excluded from the population PK analysis with reasons for their exclusion documented in the modelling report.

The final model may be re-run as a sensitivity analysis with and without the inclusion of these outlying data. Parameter estimates from these two models will then be compared to justify outlier exclusion and may be included as an appendix item in the population PK analysis report(s) where appropriate. The proportion of outliers should be low and can be excluded from the analysis given their potential to negatively impact convergence and/or parameter values.

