## 5.2. Confirmation of Dosing Regimen in Adolescent Participants

[figure not shown]
The criterion used for exploring the consistency between simulated data in adults and plasma concentration data in the available adolescents participants will be that >50% of the observed concentrations in the specified age group of pediatric participants is included in the 95% prediction intervals of the simulated data in adults at 2 mg.

The 95% prediction intervals of the simulated data in adults are shown in Figure 2 (together with simulated observations in a panel of 4 participants); 95% prediction intervals of adult daprodustat plasma concentrations following repeated dose of 2 mg are also reported in Table in the Appendix.

If the consistency between predicted and observed concentration data will be ensured (see Figure 2, where only 4 out of 16, i.e., 25% of the observed plasma concentrations are outside the predefined prediction intervals), the outcome of the previously defined pediatric simulations can be considered adequate. Therefore, it can be concluded that the dosing regimen proposed in adolescents (equivalent to that applied to adult participants) is reasonable. Based on this information, it might also be inferred that the starting dose foreseen by the protocol for participants 6-<12 years old (starting dose of 1 mg QD subsequently titrated based on hemoglobin levels) is reasonable.

If the consistency between observations and predictions will not be ensured, then the popPK model (see Section 5.1) may be used (after suitable modifications, as required) to propose a different dose to be used in adolescents and/or in participants in the lower pediatric age ranges.

Figure 2. Overlay of Simulated Daprodustat Plasma Concentrations in Virtual Pediatric Participants after Repeated Dosing of Daprodustat (Normalized to a Dose of 2 mg QD) on the 95% Prediction Interval of Daprodustat Plasma Concentrations in Adults [3].

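### The PK plan allows a concentration to be excluded for differing from other individuals' values, with no documented error, threshold or with/without comparison; with four adolescents this could remove genuine variability.

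*SAP*

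**What the plan says.** Section 4.3 (Data Handling) of the population PK analysis plan opens: "Data records may be considered for exclusion based on the following reasons". The first reason is "The value is inconsistent with that for other individuals or with the chronological sequence of study procedures", completed by "and cannot be resolved through a query resolution process". The other three reasons are inadequate supporting information, documented errors in dosing, sampling, handling or assay, and outliers under Section 4.3.5. The section also promises disclosure: "A listing of all missing and excluded data, together with a reason for their exclusion will be provided as an appendix" to the report.

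Section 4.3.5 flags concentrations with an absolute conditional weighted residual above 6 and adds: "These data may be excluded from the population PK analysis with reasons for their exclusion documented in the modelling report". A re-run with and without these outliers is optional.

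Section 4.1 ties the analysis dataset to Section 5. That section holds both the model-based description (5.1) and the dose check (5.2), which sets out "The criterion used for exploring the consistency between simulated data in adults and plasma concentration data in the available adolescents participants". Sections 1.2 and 5.2 describe the check as using available, or observed, concentrations and do not say whether Section 4.3 exclusions apply. Sections 2 and 3 record four adolescents, with the dialysis and non-dialysis sub-trials taken together.

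**The concern.** Disagreement with other individuals is a ground based on the measured value itself. Because it stands apart from documented error and from the residual-based outlier rule, it reaches values that neither of those would touch. Among the study participants, the other individuals are three people.

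The query condition protects only in part. A site can confirm dose, time and sample, but it cannot make a correct value agree with other children's values. A confirmed extreme value could therefore still be called inconsistent and unresolved.

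The exercise is meant to describe adolescent exposure and compare it with adults, so an unusually high or low exposure is among the most informative data it can collect. If such a value were removed, the exposure summary would move towards participants who resemble one another and the apparent spread would shrink. The listing would disclose the removal but would not show the result with the value included.

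**Working it through.** **The plan's own figure.** Section 5.2 illustrates the check with 4 of 16 concentrations outside the interval: 4/16 = 25%, which reproduces. Sixteen is 4 participants × 4 repeat-dose samples. Adding the 3 Day 1 samples gives 4 × 7 = 28. Both counts assume complete sampling.

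**How different are genuine values?** Inputs are the 2.5th and 97.5th percentiles in Appendix Table 2 of the PK plan, taken as log-normal, with log-SD = ln(P97.5/P2.5)/(2 × 1.96).
- 1.5 h: 88.58/6.03 = 14.7-fold; log-SD 0.69.
- 4 h: 36.26/0.498 = 73-fold; log-SD 1.09.

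In 200,000 simulated sets of four genuine values, the median ratio of largest to smallest is 3.9 at 1.5 h and 8.7 at 4 h. The chance that an extreme value lies at least 3-fold from its nearest neighbour is 18% at 1.5 h and 48% at 4 h, with nothing wrong.

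**Effect of one exclusion on raw summaries.** Inputs come from Appendix Table 1 of the PK plan.
- Phase 2/3 model: CL CV 75%, so participant log-SD = √ln(1 + 0.75²) = 0.67; residual log-SD 0.979.
- Phase 1 model: CV 16.8%, so 0.17; residual 0.47 (a proportional SD treated as log-scale).

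The simulation used 40,000 trials of 4 participants × 4 samples. The participant effect was applied equally at every time point. The geometric mean weights participants equally, and SD is the mean SD of participants' mean log values. As a check on the starting SD: √(0.668² + 0.979²/4) = 0.828, times the small-sample factor 0.921 for n = 4, gives 0.76.

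Most discordant single record removed:
- Phase 2/3: median shift 1.10-fold; shift above 10% in 52% of trials; SD 0.76 to 0.66 (0.66/0.76 = 0.87, a fall of 13%).
- Phase 1: 1.05-fold; 4% of trials.

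Most discordant whole participant removed (worst case):
- Phase 2/3: 1.37-fold; 97% of trials; SD 0.76 to 0.43 (a fall of 43%).
- Phase 1: 1.12-fold; 62% of trials; SD 0.27 to 0.15.

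Every simulated trial makes an exclusion, so these are sizes given that the rule is used. Weighting all remaining records equally, instead of participants, gives a somewhat larger single-record shift.

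**Effect on the dose check.** With k of n values outside and m outside values removed, the share outside becomes (k − m)/(n − m).
- Section 1.2 rule (inadequate if more than 50% are outside), n = 16. One removal: 9/16 = 56.3% becomes 8/15 = 53.3%, still a failure. Two removals: 7/14 = 50%, reversed. Four removals: 9/16 becomes 5/12 = 41.7% and 10/16 becomes 6/12 = 50%, both reversed; 11/16 becomes 7/12 = 58.3%, not reversed.
- Section 5.2 rule (more than 50% must be inside). One removal reverses only k = 8: 8 of 16 inside becomes 8 of 15, or 53.3%.
- n = 28: up to four removals reverse only k = 15 or 16 (Section 1.2) or k = 14 or 15 (Section 5.2).

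Treating samples as independent, the chance of 9 or more of 16 outside is 0.7% at the illustrated 25% rate. The chance of landing on 9 or 10, the counts that four removals can reverse under Section 1.2, is 0.7% at a 25% rate, 12% at 40% and 30% at 50%. Samples within a participant are correlated, so these are rough.

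**The case against.** The rule is softer than a quick reading suggests. It is permissive, conditional on a query, and written for individual records; participant inclusion is handled in Section 4.2. Every exclusion is listed with a reason, and SAP Listing 16.22 shows concentration-time data for the All PK set. A query that confirms a value might itself count as resolution. All of this stands, and it is why the point is that the rule could remove variability, not that it does.

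Exposure will be described by post-hoc estimates from the earlier population model (Section 1.1), fitted first without re-estimation and with re-estimation only as data permit (Section 5.1). The PK estimand in protocol Section 3.1 is the geometric mean of Cmax and AUC. The raw-concentration shifts above are therefore illustrations, and the effect on post-hoc estimates would probably be smaller.

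A reader might infer that exclusions will decide the dose check. The documents do not say that Section 4.3 governs that count, and protocol Section 9.3.1 speaks of all available concentration data. Reversal also needs a count close to 50%. Recruitment has ended, so the check opens no further cohort in this study.

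A reader might also infer a conflict with the protocol, whose Integrated PK set is defined by participants "who had at least 1 nonmissing PK assessment". Those sets define participants, not record handling, and the protocol defers detail to the separate plan, so nothing is contradicted.

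What none of this answers is that a listing shows what was removed but not how the result looks with it, and the optional re-run in Section 4.3.5 does not cover this reason at all.

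**Conclusion.** The concern holds in limited form. The plan permits a value-based exclusion without a documented error, a threshold or a with/without comparison, in a sample of four where large genuine differences are expected.

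Its likely size is modest: for one record, about a 1.05- to 1.10-fold shift in the raw geometric mean and a fall of about 13% in the between-participant SD. The whole-participant figures are an upper bound that would require every sample from one child to be excluded. These figures assume log-normality, complete sampling, variability as in the earlier adult models, and that the exclusion is actually made.

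The dose check is rarely affected. Under Section 1.2 at least two removals near the cut-off are needed to reverse a failure.

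The residual rule in Section 4.3.5 has a numeric threshold and documented reasons. Barring it from the main analysis would be a preference, not a correction.

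**What to change.** - **Section 4.3:** delete disagreement with other individuals' values as a stand-alone reason. Keep chronology conflicts, inadequate supporting information, and documented dosing, sampling, handling or assay errors.
- **Section 5.2:** state that the in/out count uses every reported concentration with a known dose and time. While editing, reconcile Sections 1.2 and 5.2 at exactly 50%: 8 of 16 outside is adequate under the first and not consistent under the second.
- **Section 4.3.5:** make the re-run with and without mandatory for any value-based exclusion, including those flagged by the residual threshold, and report both results. The residual rule may otherwise stay as planned.

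The cost is a few lines of wording and one extra model run if a value is excluded. The downside is a possibly less smooth fit and wider variability estimates.

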## 4.3.1. Missing Dose Information

Records with missing dosing times will be excluded from the analysis. Where appropriate and justifiable, missing dose amount may be imputed using nominal values. However, care will be taken to ensure that "missing" doses are not due to non-compliance or other clinical decisions such as modification due to treatment-emergent adverse events. Dosing data that cannot be imputed will be flagged and excluded from all analyses.

## 4.3.2. Missing Observations

Concentration and/or time data identified as missing will be handled as follows:

- Missing observations and/or sampling times will be excluded from the analysis.
- Observations immediately prior to the first dose (pre-dose) will be retained in the dataset and flagged for exclusion.
- Concentrations associated with missing dosing data will be flagged and excluded.

## 4.3.3. Missing Covariates

Intrinsic or extrinsic covariate data that are missing will be handled as follows:

- Missing continuous covariates at baseline may be imputed using the median value of the full analysis population or appropriate sub-category.
- If appropriate, time-varying continuous covariates identified as missing will be imputed using a last-observation carried forward rule.
- Missing categorical covariates will either be assigned to an independent "missing" category or combined with a relevant subgroup.
- Unlikely covariate values, such as those well outside of an expected range, will be considered on a case-by-case basis.

If the percentage of missing data exceeds 10%, that covariate will be excluded from the analysis, and only assessed for data exploration purposes.

#### 4.3.4. Data Below the Limit of Quantitation

Concentrations reported as below the limit of quantitation (BLQ) will be retained in the analysis dataset and flagged using an independent column. If greater than 15% of post dose concentrations are BLQ, these samples maybe treated as censored, and a likelihood-based approach maybe be used to handle these data [7,8]. The approach to handling of BLQ data will be described and justified in the report.

## 4.3.5. Handling of Outlier Data

Prior to population PK analysis, graphical inspection will be conducted of individual or pooled concentration-time profiles to identify outlier or anomalous data. Additionally, the PK data may be plotted relative to each analysis participant's actual dosing history to detect any anomalies. Following preliminary model runs, concentrations for which the absolute value of conditional weighted residuals (CWRES) are greater than 6 (|CWRES > 6|) will be flagged as questionable. These data may be excluded from the population PK analysis with reasons for their exclusion documented in the modelling report.

The final model may be re-run as a sensitivity analysis with and without the inclusion of these outlying data. Parameter estimates from these two models will then be compared to justify outlier exclusion and may be included as an appendix item in the population PK analysis report(s) where appropriate. The proportion of outliers should be low and can be excluded from the analysis given their potential to negatively impact convergence and/or parameter values.

## 5. ANALYSIS METHODS

## 5.1. Population PK Assessment

A previously developed population PK model will be used to characterise the pharmacokinetics of daprodustat in adolescent patients.

The most recent version of the population PK model of daprodustat, with all the meaningful covariates that were identified, will be used as an initial step to fit the PK data from the paediatric study (e.g., using MAXEVAL=0 option in NONMEM), re-estimation of allometric coefficients, and other parameters may be considered as data permit. All covariate effects identified previously, and retained in the comprehensive population PK model (Section 1.1.3) will be kept in the model. Covariates may be challenged to justify their retention in the model.

## 5.1.1. Model Qualification

The final population PK model will be considered appropriate based on a combination of acceptance criteria and standard diagnostic GOF plots [9]. Acceptability of the model will preferably include stability, convergence, a successful covariance step, and/or low condition number (e.g., <1000). If the condition number ranges between 1000 and 10000, the model will be considered on a case-by-case basis. Other model suitability criteria may include parameter plausibility, and low relative standard errors (RSE, e.g., <30% for fixed effect parameters and <50% for random effect parameters).

Several standard GOF plots will be used to visualize agreement between observed versus model-predicted values and lack of bias. These may include the following:

- Observed versus individual predicted (IPRED) concentrations.
- Observed versus population predicted (PRED) concentrations.
- CWRES versus PRED and time since first dose and/or last dose.
- IPRED versus absolute individual weighted residuals (IWRES).

- ETA-ETA correlations and distribution of inter-individual random effects.
- CWRES and normalized prediction distribution error (NPDE) distributions.

In addition to the above GOF diagnostic plots, the performance of the final population PK model will be evaluated using a visual predictive check (VPC).

## 5.2. Confirmation of Dosing Regimen in Adolescent Participants

[figure not shown]
The criterion used for exploring the consistency between simulated data in adults and plasma concentration data in the available adolescents participants will be that >50% of the observed concentrations in the specified age group of pediatric participants is included in the 95% prediction intervals of the simulated data in adults at 2 mg.

The 95% prediction intervals of the simulated data in adults are shown in Figure 2 (together with simulated observations in a panel of 4 participants); 95% prediction intervals of adult daprodustat plasma concentrations following repeated dose of 2 mg are also reported in Table in the Appendix.

If the consistency between predicted and observed concentration data will be ensured (see Figure 2, where only 4 out of 16, i.e., 25% of the observed plasma concentrations are outside the predefined prediction intervals), the outcome of the previously defined pediatric simulations can be considered adequate. Therefore, it can be concluded that the dosing regimen proposed in adolescents (equivalent to that applied to adult participants) is reasonable. Based on this information, it might also be inferred that the starting dose foreseen by the protocol for participants 6-<12 years old (starting dose of 1 mg QD subsequently titrated based on hemoglobin levels) is reasonable.

If the consistency between observations and predictions will not be ensured, then the popPK model (see Section 5.1) may be used (after suitable modifications, as required) to propose a different dose to be used in adolescents and/or in participants in the lower pediatric age ranges.

Figure 2. Overlay of Simulated Daprodustat Plasma Concentrations in Virtual Pediatric Participants after Repeated Dosing of Daprodustat (Normalized to a Dose of 2 mg QD) on the 95% Prediction Interval of Daprodustat Plasma Concentrations in Adults [3].

## 6. REPORTING

A regulatory compliant standalone population PK report will be developed that details the aims, methods, results, conclusions, and any other supporting information [10]. Key modelling decisions, final NONMEM output (.lst) files, and other relevant code will be included as Appendices. The final report(s) will undergo QC by an independent reviewer that will assess scientific accuracy and appropriate document formatting.

